1.3 Possible risks

Adverse reactions of vitamin K1: occasionally allergic reactions. Mainly occurs when the intravenous injection is too fast, more than 5mg/ minutes can cause facial flushing, sweating, bronchospasm, tachycardia,

hypotension, etc., serious allergic reactions may endanger life. Intramuscular injection can cause redness and swelling. The newborn may suffer from hyperbilirubinemia, jaundice and hemolytic anemia after the use of the product.

.1.4. Benefits

Cerebral hemorrhage is a common disease in Department of neurosurgery. It is an important measure to reduce the mortality and disability rate in the acute stage. Vitamin K1 may reduce the risk of rebleeding in patients with intracerebral hemorrhage, and the amount of brain bleeding is directly related to prognosis. Effectively reduce the amount of intracerebral hemorrhage, improve the prognosis, reduce the length of stay, reduce the time of admission to ICU and reduce the mortality.

2 Test purpose

The effectiveness and safety of vitamin K1 were mainly targeted at patients with cerebral hemorrhage (non aneurysm or vascular malformations, rupture, bleeding). To observe whether vitamin K1 can effectively avoid the increase of cerebral hemorrhage and improve the prognosis.

3 Test design

The study included spontaneous hypertensive intracerebral hemorrhage at super tentorium of cerebellum patients as the research object, to exclude cerebral aneurysms or cerebral hemorrhage, venous malformation of abnormal liver function, taking anticoagulants or antiplatelet drugs in patients. The study was divided into the experimental group and the control group, and a multicenter randomized controlled trial was conducted. In the use of a etamsylate intravenous infusion of 0.5g of patients admitted to hospital within 8 hours later, the experimental group in the incidence of cerebral hemorrhage within 2 days after the daily intravenous infusion of vitamin K1 20mg, the control group received intravenous saline, all patients were no longer use other hemostatic agents. The efficacy and safety of vitamin K1 in the early onset of cerebral hemorrhage were assessed by the observation between two groups.

A randomized, single blind, positive / placebo parallel control, multicenter, clinical trial design was used. The treatment lasted for 2 days and followed up for 6 months.

4 Subjects recruited and exited

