4.2 Inclusion criteria

1) Patients with spontaneous intracerebral hemorrhage (enhanced by cerebral arterial CT or cerebral angiography confirmed rupture of non aneurysm or arteriovenous malformation);

3) Age 18-65 years, male or not pregnant female;

4) GCS score at admission;

5) Head CT or MRI examination confirmed cerebral hemorrhage at super tentorium of cerebellum and the amount of bleeding in 10ml-45ml (Duotian formula to calculate the hemorrhage volume);

6)During the hospitalization, no urokinase and other hemostatic drugs were used except for the use of K1 and vitamin D in the project;

7) Informed consent form signed by the patient's family.

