7.5.3 Medication and treatment are permitted

(1) The other combined diseases without affecting the curative effect and safety evaluation, can be symptomatic medication, but it must be the case report form to record the medicine general or other treatment, dosage, reason, use frequency and time etc, so as to summarize, analyze and report.

⁽²⁾The follow-up period can use cognitive rehabilitation methods, including occupational therapy, implicit memory rehabilitation, errorless learning, cognitive neuropsychological rehabilitation, rehabilitation and computer assisted cognitive rehabilitation, virtual remote control via the Internet, and the electromagnetic stimulation, should be recorded in detail in CRF.

⁽³⁾The combination drugs used for adverse events during the trial should be recorded in CRF.

8 Therapeutic evaluation standard

Main outcome measures: the amount of intracerebral hemorrhage (0d, 1D, 3D, 7D) at each time after the onset of disease.

Main outcome measures: (1) the amount of the time changes in blood coagulation, platelet levels and GCS scores after the onset (0d, 1D, 3D, 7D); (2) days in ICU; (3) the total hospitalization days; (4) complications including neurological complications, complications, blood coagulation circulatory complications after cerebral hemorrhage; (5) 1m and 6m mRS score.

9 Safety evaluation

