Statistical analysis plan

1. Statistical software

Using STATA version 12.0 statistical software.

2. Special data processing

(1) Missing data: When a certain important data due to loss, miss follow-up, examination is happen, the LOCF method will be adopted to carry out the data and the secondary index will not be transferred.

(2) Outlier data: According to statistical and medical analysis, determine these data will be included or not. Sensitivity analysis was conducted for the outliers of the main targets, including two results consistent with those who did not outliers.

3. Selection of inspection level α and power of test β

(1) Difference test: With $\alpha = 0.05$ as the test standard, two-sided test was adopted, and the statistical methods, statistics and specific P values were given. $P \leq 0.05$ was considered statistically significant.

(2) Superiority test: Based on a power of 80% ($\beta = 0.2$), $\alpha = 0.025$ was conducted for the one-sided test. The difference between the groups and the 95% confidence interval of the mRS score difference to the baseline values after treatment in the experimental group and the placebo group was calculated by the least square method. If the 95% confidence interval between the two groups was greater than 0, the experimental group can be thought to be superior to the placebo group, otherwise not.

4. Statistical expression

(1) The statistical report mainly expressed in form, which was self-evident. It had the title, the heading and the number of cases, the necessary remarks and the text of statistical results and the description of data results.

(2) Descriptive statistics: The measurement data is described by mean number, standard deviation, maximum value, minimum value, 95% confidence interval, median, Q1 and Q3. The enumeration data is described by frequency (constituent

ratio), and corresponding statistics and P value are calculated.

(3) Inferential statistics: Measurement data were compared between groups by analysis of variance or K-W rank-sum test according to the distribution pattern. Enumeration data were compared between groups by R*C Chi-squared test and Fisher exact test. The ranked data was tested by CMH. The main/important therapeutic effect index will use the baseline for the covariant, considering center, operation or not after injury for analysis of covariance.

5. Specific statistical analysis content

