(1) Analysis of program implementation: a list was adopted to summarize the entry and completion of all and each central cases, and tabulate details and the data collation of those cases which are not meet the inclusion criteria, fall off, low compliance, against therapy and drug combination, interview time beyond window.

(2) Analysis the patient compliance and the drug combination during the trail.

(3) Condition of each analysis data set: Based on the analysis of the implementation of the program, determining the data imputation of each deviated test programme case. Summarize the cases of each analysis data sets, such as per-protocol set (PPS), full analysis set (FAS), safety set (SS).

(4) Baseline equalization analysis: Compare the baseline data of demographic data, vital signs and medical history related features.

(5) Analysis of curative effect index :

1) Compare the changes of mRS score to the baseline after using the drug in 2 days, followed up with 1 month and 6 months in the two groups. The main/important therapeutic effect index will use the baseline for the covariant, considering center, operation or not after injury for analysis of covariance. The covariance analysis was performed on the change of mRS score at baseline after 6 months of follow-up. The difference between the groups and the 95% confidence interval of the mRS score difference to the baseline values after treatment in the experimental group and the placebo group was calculated by the least square method. If the 95% confidence interval between the two groups was greater than 0, the experimental group can be

thought to be superior to the placebo group, otherwise not.

2) Compare the changes of cerebral hemorrhage amount to the baseline in the two groups.

3) Compare the changes of coagulation function, platelet level and GCS score to the baseline in the two groups.

4) Compare the number of days stayed in the ICU and the hospital in the two groups.

(6) Safety analysis:

Compare the incidence and classification rate of complications, adverse events and adverse reactions during the test in the two groups, and list the details of each adverse event, such as the detailed occurrence, outcome and the relationship with drugs.

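### SAP 2(2) leaves outlier exclusion to unblinded judgement and names no primary version; for haematoma volume this can bias the comparison in either direction, by an amount the documents cannot fix

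*SAP*

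**What the plan says.** SAP section 2(2) is the whole outlier rule. Inclusion is settled case by case: "According to statistical and medical analysis, determine these data will be included or not". The next sentence adds a check: "Sensitivity analysis was conducted for the outliers of the main targets, including two results consistent with those who did not outliers". The translation is poor. The likely meaning is that results with and without outliers are compared for consistency.

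Four other places bear on it:

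- Protocol section 2 states the aim: "To observe whether vitamin K1 can effectively avoid the increase of cerebral hemorrhage and improve the prognosis".
- Protocol section 8 lists "Main outcome measures: the amount of intracerebral hemorrhage (0d, 1D, 3D, 7D) at each time after the onset of disease". A second list there, which includes GCS and mRS, carries the same label.
- SAP section 5(5) puts its detailed analysis on disability: "The covariance analysis was performed on the change of mRS score at baseline after 6 months of follow-up". The superiority criterion is attached to that outcome. Volume gets one line: "Compare the changes of cerebral hemorrhage amount to the baseline in the two groups".
- Protocol section 3 describes the trial as single blind. Neither document describes a blinded data review.

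**The concern.** An outlier rule is harmless when it removes recording errors. This one does not ask whether the value is an error, and it can be applied after the data, and possibly the arm, are known.

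That matters most for haematoma volume. Change in volume is plausibly a mixture: most patients change little and a minority bleed further. Protocol 4.2 limits entry to "the amount of bleeding in 10ml-45ml", so a very large later volume will mostly reflect growth after entry. An extreme increase is then usually the event under study, and removing it as an outlier removes outcome data.

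Two different harms follow. If the rule is applied without regard to arm, the arm with more expansions loses more patients and the difference shrinks. If the person deciding knows the arm, exclusions can be chosen, and a false benefit becomes possible. The planned sensitivity analysis would show a disagreement but not settle it, because the SAP does not say which result governs.

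**Working it through.** The plan has no figure to reproduce. It states no sample size, effect size, SD, expansion rate or outlier threshold. The only check available is that the two alpha statements in SAP section 3 agree: one-sided 0.025 and two-sided 0.05 share the critical value 1.960. Everything below rests on assumed inputs.

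**Arm-blind deletion.** Assumptions: 20% of control and 12% of vitamin K1 patients expand; expanders' growth is log-normal with mean 15 ml and log-SD 0.5; non-expanders' change is normal with mean 0.5 ml; limits are taken from the pooled data.

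True difference (control minus vitamin K1) = (0.20 − 0.12) × (15 − 0.5) = 0.08 × 14.5 = 1.16 ml.

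The input that matters most is the non-expander SD, so it is varied. With a 3-SD rule, 73% to 83% of the effect remains as that SD goes from 1.5 to 5 ml, that is 1.16 × 0.73 = 0.85 ml to 1.16 × 0.83 = 0.96 ml. With a 3×IQR rule (simulated, good to about one percentage point):

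| Non-expander SD (assumed) | Effect kept | Difference left |
|---|---|---|
| 1.5 ml | about 20% | 1.16 × 0.20 = 0.23 ml |
| 3 ml | 66% | 1.16 × 0.66 = 0.77 ml |
| 4 ml | 83% | 1.16 × 0.83 = 0.96 ml |
| 5 ml | 91% | 1.16 × 0.91 = 1.06 ml |

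The reason is simple. The IQR of the non-expanders alone is about 1.35 × 1.5 = 2.0 ml at the low end and 1.35 × 5 = 6.8 ml at the high end. In the first case the limit falls among the expansions; in the second it lies beyond nearly all of them. At 1.5 ml the rule drops 13.8% of control and 8.3% of vitamin K1 patients. If all of these are expanders, that is 13.8/20 = 69% and 8.3/12 = 69% of the expanders in the two arms. At 4 ml it drops 1.7% and 1.0%.

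Power of a two-sided t-test at 0.05, with an assumed 200 per arm, falls under the 3×IQR rule from about 45% to 15% at SD 1.5 ml, but only from about 36% to 34% at SD 4 ml. Under the 3-SD rule at 1.5 ml it is nearly unchanged (about 46% to 44%), although the estimate is still biased.

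**Other assumptions.** At 30% versus 20% expansion and SD 1.5 ml, 85% (3 SD) or 62% (3×IQR) remains. If the drug instead makes expansions one third smaller without preventing them, a 3-SD rule loses 35–74% of the effect, and looser rules can reverse its sign. If the drug shifts every patient equally and the data are normal, the loss is 0–23%.

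**Deletion with the arm known.** Assume no true effect, 100 per arm and the same kind of mixture. Dropping only the 1, 2 or 3 largest increases from the treated arm raises the one-sided error from 2.5% to about 4.9%, 8.4% or 13.6%.

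**mRS.** The scale runs from 0 to 6. With an assumed mean of 3.28 and SD of 1.73, the ends lie 3.28/1.73 = 1.9 and (6 − 3.28)/1.73 = 1.6 SD from the mean, so neither a 2-SD nor a 3-SD rule flags any score. Change scores were not simulated.

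**The case against.** The SAP asks for medical as well as statistical analysis. A reviewer who sees an expansion confirmed on CT would be expected to recognise it as real and keep it. The simulations model automatic cut-offs, which the SAP does not prescribe. A sensitivity analysis is also planned, and SAP section 4(3) already allows a rank test, which limits the influence of extreme values and so the motive for removing them. All of this stands, and it lowers the likely harm. It does not close the gap: nothing obliges the reviewer to keep a true value, to decide before knowing the arm, or to treat one version as primary.

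Three stronger readings are tempting, and the documents support none of them.

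- A reader might infer that the rule will remove most of the treatment effect. The 20% figure depends on a non-expander SD of 1.5 ml, which nothing in the documents supports; at 5 ml, 91% remains.
- A reader might infer that the bias always runs toward no difference. That holds for arm-blind deletion in the main scenario, not for deletion with the arm known. Protocol 6.1.4 also allows surgical removal of the haematoma, so large falls can be flagged too.
- A reader might infer that the SAP's superiority conclusion is at risk. That conclusion rests on change in mRS, a bounded scale on which outliers are unlikely.

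**Conclusion.** The point holds for haematoma volume, as a defect in the rule rather than a demonstrated loss. SAP 2(2) permits true values to be excluded after the data are seen, without blinding and without a named primary version, on an outcome whose extreme increases are largely the events of interest. Some effect was lost under arm-blind deletion in every expansion scenario examined. The amount ranges from minor to severe with the unstated threshold, expansion rate, measurement spread and drug mechanism, and no single percentage should be attached to this trial. Selective deletion could inflate false positives several-fold with only two or three patients removed: 8.4/2.5 = 3.4 times and 13.6/2.5 = 5.4 times in the assumed case.

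It is also unclear which outcome the sensitivity analysis covers, because the protocol lists volume first among its main outcomes while the SAP builds its superiority test on mRS. The change should be made, since it is cheap and removes both harms, but the plan does not fail on this point alone.

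**What to change.** Replace SAP 2(2) with:

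*All recorded values enter the primary analysis. A value is corrected or set to missing only if checking against the source scan or record shows it is an error, decided before the arm is known. Analyses without statistical outliers are sensitivity analyses only.*

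State in the same paragraph which outcome is the main target, so that protocol section 8 and SAP section 5(5) agree. No new rank-based analysis is needed, since SAP section 4(3) already allows one.

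The cost is one SAP paragraph and a blinded check of flagged scans against source. The statistical downside is somewhat larger variance from the extreme values that are kept.

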1.1.1 Epidemiological of cerebral hemorrhage

Cerebral hemorrhage is a kind of acute onset, rapid change, serious disease, which accounts for about 10%-25% of cerebrovascular disease, disability rate and fatality rate were 70%-80%, 38%-43%, the recurrence rate was about 1 1.8%-11%. Hypertension and amyloid cerebrovascular disease are the main causes of primary spontaneous intracerebral hemorrhage, and hypertension is the most common risk factor for intracerebral hemorrhage. Cerebral hemorrhage not only has a serious impact on patients, but also brings heavy burden to society and family. The treatment of cerebral hemorrhage is complicated , which is one of the stroke which is proved by evidence-based medicine to be effective. Standardized treatment and effective integrated management can significantly reduce the fatality rate and improve the outcome of intracerebral hemorrhage.

Delayed cerebral hemorrhage is one of the important reasons for the aggravation of cerebral hemorrhage . The amount of hematoma in patients with intracerebral hemorrhage is closely related to the secondary injury of nerve function, which directly affects the prognosis of patients. Delayed cerebral hemorrhage is closely related to coagulation dysfunction. The prevention of delayed hemorrhage is an important part in the treatment of cerebral hemorrhage. The blood coagulation is initiated immediately after Acute intracerebral hemorrhage, and the coagulation process is divided into three stages: prothrombin complex formation, prothrombin activation, and fibrin formation. Synthesis of Coagulation factor FX, F II, F VII and F IX are dependent on vitamin K1. Vitamin K1 can cause the formation of prothrombin complex, clot solid, effectively blocking the vascular rupture, so that the amount of bleeding decreased. However, while controlling bleeding, the risk of thrombosis may be induced, and how to effectively control bleeding and avoid thrombosis is often a clinical problem.

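### For harms, the SAP's only between-group inference is a P value at 0.05, with no risk difference or ratio and no interval; for uncommon harms a non-significant result would say little about safety

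*SAP*

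**What the plan says.** Protocol section 2 (Test purpose) pairs the two aims: "The effectiveness and safety of vitamin K1 were mainly targeted at patients with cerebral hemorrhage". Section 3 (Test design) adds how they are judged: "The efficacy and safety of vitamin K1 in the early onset of cerebral hemorrhage were assessed by the observation between two groups". The background (1.1.1) names a specific harm, that "while controlling bleeding, the risk of thrombosis may be induced". Section 1.3 describes allergic reactions as occasional, and serious ones as potentially life-threatening.

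The SAP handles event data as follows:

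- **3(1), difference tests:** "With $\alpha = 0.05$ as the test standard, two-sided test was adopted", with P of 0.05 or less counted as significant.
- **4(2), description:** measurement data receive a 95% confidence interval among their summaries. For event data the list is shorter: "The enumeration data is described by frequency (constituent" "ratio), and corresponding statistics and P value are calculated".
- **4(3), comparison:** "Enumeration data were compared between groups by R*C Chi-squared test and Fisher exact test".
- **5(6), safety:** "Compare the incidence and classification rate of complications, adverse events and adverse reactions during the test in the two groups", plus a listing of each adverse event with its outcome and relationship to the drug.

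The only between-group interval in the SAP is the one for change in mRS (3(2) and 5(5)1). The 80% power is stated in 3(2), under the superiority test. No power, margin or interval is stated for any safety comparison.

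**The concern.** A test of no difference can show that harm is present. When it is not significant, it cannot show that harm is absent or small. That needs an estimate of the excess risk and its upper confidence limit. The SAP supplies an interval for measurement data and for mRS, but not for the event rates on which the safety aim depends.

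Allergic reactions are uncommon on the protocol's own wording, and thrombosis may be. If such an event were more frequent on vitamin K1 but P exceeded 0.05, the prespecified inferential result would be that no significant difference was found. No prespecified output would tell the reader what excess the data still allow, in a trial whose background presents the balance between bleeding and thrombosis as the clinical problem.

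**Working it through.** **1. What the text settles.** Side by side, SAP 4(2) lists an interval for measurement data and none for event data. 4(3) and 5(6) add only tests, frequencies and a listing. This needs no assumption.

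**2. Inputs for the size of the problem.**

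- From the SAP: two-sided 0.05; chi-squared and Fisher tests.
- Not in the documents, so assumed: patients per arm, 1:1 allocation, and the control rate of each harm.
- Assumed sizes: the number per arm giving 80% power for a standardised mean difference d in a two-sample t test (noncentral t, two-sided 0.05). This gives 64 (d = 0.5), 100 (0.4), 176 (0.3) and 394 (0.2). Using mRS to set the size is itself an assumption. Protocol section 8 lists haemorrhage volume first among the main outcomes, and no document says which endpoint, if any, set the size.

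**3. Method.** The two arms are independent binomials, X on saline ~ Bin(n, p) and Y on vitamin K1 ~ Bin(n, 2p). All pairs (X, Y) are enumerated. Fisher's test is used when the smallest expected count is below 5, and the uncorrected chi-squared test otherwise. The SAP names both tests without a switching rule, so this rule is also assumed. Miss rate = 1 − Pr(P ≤ 0.05 and Y > X).

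**4. Chance of missing a true doubling.**

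| Saline vs vitamin K1 | 64/arm | 100/arm | 176/arm | 394/arm |
|---|---|---|---|---|
| 2% vs 4% | 99% | 95% | 84% | 62% |
| 3% vs 6% | 95% | 88% | 73% | 47% |
| 5% vs 10% | 84% | 73% | 57% | 23% |
| 10% vs 20% | 65% | 48% | 24% | 2% |
| 20% vs 40% | 29% | 12% | 1% | about 0% |

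By the normal approximation to the chi-squared test, 50% power for a doubling needs 559 per arm at a 2% control rate, 214 at 5% and 98 at 10%. For 80% power the figures are 1,141, 435 and 199.

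The one serious-outcome rate in the documents that could anchor a scenario for death is the background fatality of 38% to 43% (1.1.1). A doubling from 38% to 76% is missed in under 1% of trials at 64 per arm.

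**5. What the interval would add (assumed counts).** Take 6/100 events on vitamin K1 and 3/100 on saline.

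- The smallest expected count is (6 + 3)/2 = 4.5, so Fisher's test applies: P = 0.50.
- The risk difference is 6.0% − 3.0% = 3.0 points.
- The Wilson limits are 2.78% to 12.48% for 6/100 and 1.03% to 8.45% for 3/100.
- Newcombe lower limit: 3.0 − √[(6.00 − 2.78)² + (8.45 − 3.00)²] = 3.0 − 6.3 = −3.3 points.
- Newcombe upper limit: 3.0 + √[(12.48 − 6.00)² + (3.00 − 1.03)²] = 3.0 + 6.8 = +9.8 points.

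The P value reads as no significant difference. The interval shows that an excess of nearly 10 points is not excluded.

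**The case against.** The strongest reply is that the numerical consequence cannot be derived from the documents. They give no sample size, allocation ratio or harm rate. Low rates have some support for allergy, none for thrombosis, and cannot be presumed for complications as a whole, which protocol section 8 defines broadly. This stands. A reader might infer that the test would usually miss a doubling of serious harm; the table supports that only for uncommon events in a small or moderate trial. At 394 per arm a doubling from 3% or 5% is detected more often than not, and doublings of common events are rarely missed at 100 or more per arm.

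A second reply is that the P value is not the trial's only safety answer. This also stands: frequencies by group and an event listing with outcome and causality are planned, and protocol section 5 allows the trial to stop for serious safety problems with no P-value condition. A reader could compute an interval from the published counts. But neither the listing nor the frequencies are a between-group estimate with its uncertainty, and nothing in the plan requires one.

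Third, the SAP nowhere says that P above 0.05 means safe; its one explicit decision rule concerns mRS. That is correct. The point is that the plan leaves this reading open, not that it prescribes it. Nor may the miss rates be held against a 20% ceiling, since the stated 80% power belongs to the superiority test.

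Finally, an interval without an acceptable excess gives no decision rule. True, but it states what the data allow, which the P value does not.

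**Conclusion.** The point holds in conditional form. On the text alone, the SAP's only between-group inferential result for harms is a P value at 0.05, although safety is a stated aim and intervals are planned elsewhere. How much this matters depends on assumptions about size and event rates. At control rates of 2% to 5%, a doubling is missed in 57% to 99% of trials with 64 to 176 per arm and in 23% to 62% with 394 per arm. At 20% or more, with at least 100 per arm, the figure is 12% or less. For uncommon harms a non-significant P would therefore carry little information, and no planned output would bound the remaining excess. The documents do not support saying that the plan equates non-significance with safety, or that the test fails for harms in general. The change should be made; it is a gap in analysis and reporting, not a flaw in the trial's design.

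**What to change.** In SAP 4(2) and 5(6), add the between-group risk difference (vitamin K1 minus saline) with its 95% confidence interval, by Newcombe's method or an exact method when events are sparse. Report it for complications, adverse events, serious adverse events (which 5(6) does not name separately), thrombotic events and allergic or infusion reactions. The tests in 4(3) can stay.

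Add a sentence to 5(6) to this effect: *A P value above 0.05 will not be taken as evidence of safety; the upper limit of the 95% interval for the excess risk will be stated for each harm category.*

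The cost is SAP wording and one extra column in the safety tables, with no new data or patients. The safety statement may look less favourable, because intervals for rare events are wide.

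### The baseline- and centre-adjusted ANCOVA is spelled out only for mRS; coagulation, platelets and possibly haemorrhage volume are left to unadjusted change scores and an unspecified choice of test

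*SAP*

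**What the plan says.** SAP 4(3) gives a general rule for continuous outcomes: "Measurement data were compared between groups by analysis of variance or K-W rank-sum test according to the distribution pattern". It names no normality test, threshold, decision time or blinded review.

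The same paragraph then makes an exception: "The main/important therapeutic effect index will use the baseline for the covariant, considering center, operation or not after injury for analysis of covariance". SAP 5(5)1) repeats that sentence and attaches it to one outcome: "The covariance analysis was performed on the change of mRS score at baseline after 6 months of follow-up". The list of outcomes that count as 'main/important' is not given.

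The remaining efficacy items name no model:

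- SAP 5(5)2): "Compare the changes of cerebral hemorrhage amount to the baseline in the two groups".
- SAP 5(5)3): "Compare the changes of coagulation function, platelet level and GCS score to the baseline in the two groups".
- SAP 5(5)4): "Compare the number of days stayed in the ICU and the hospital in the two groups".

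Protocol section 8 puts volume first: "Main outcome measures: the amount of intracerebral hemorrhage (0d, 1D, 3D, 7D) at each time after the onset of disease". It gives the same days, including day 0, for coagulation, platelets and GCS, and labels that second list as main outcomes too.

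**The concern.** Two things are left open.

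First, the scope of the ANCOVA. A reader cannot tell whether haemorrhage volume is adjusted for its day-0 value and centre or falls to the unadjusted default. Coagulation and platelets appear to fall to the default. For these outcomes the day-0 value enters only by subtraction, which is less precise than using it as a covariate, and differences between centres are not removed. The SAP already accepts the better method for mRS.

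Second, the choice of test. ANOVA compares means and Kruskal-Wallis compares ranks, and on skewed data they can disagree. With no criterion, the choice could differ between outcomes or between days of the same outcome. The trial is single blind, and the SAP does not say whether the person choosing the test will have seen results by arm.

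At stake are the precision and reproducibility of the non-mRS results, including the outcome that the protocol lists first.

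**Working it through.** **Inputs from the documents.** For difference tests, alpha is 0.05: "as the test standard, two-sided test was adopted" (SAP 3(1)). The superiority test uses one-sided 0.025 with 80% power (SAP 3(2)). Both give a critical value of 1.960, so they agree. The documents state no sample size, effect size, SD or baseline correlation, so there is no planned figure to reproduce. Everything below uses assumed values, and 80% is borrowed only as a reference point.

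**Change score against ANCOVA.** Let the outcome have the same variance s² at day 0 and follow-up, with correlation rho.

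- Variance of the change score: 2(1 - rho)s²
- Residual variance under ANCOVA: (1 - rho²)s²
- Ratio, ANCOVA to change: (1 - rho²) / [2(1 - rho)] = (1 + rho)/2

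A comparison with 80% power under ANCOVA has a standardised effect of 1.960 + 0.842 = 2.802. On the unadjusted change, its power is Phi(2.802 × sqrt((1 + rho)/2) - 1.960). Sample sizes per arm assume a difference of 0.4s: n = 2 × 2.802² × (variance/s²) / 0.4², rounded up. An unadjusted follow-up value needs 99 per arm.

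| rho | Variance ratio | Power on unadjusted change | n per arm, change | n per arm, ANCOVA |
|---|---|---|---|---|
| 0.3 | 0.65 | Phi(0.299) = 62% | 138 | 90 |
| 0.5 | 0.75 | Phi(0.466) = 68% | 99 | 74 |
| 0.7 | 0.85 | Phi(0.623) = 73% | 59 | 51 |
| 0.9 | 0.95 | Phi(0.771) = 78% | 20 | 19 |

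At rho = 0.3 the change score needs more patients than ignoring baseline altogether (138 against 99). The two are equal at 0.5.

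**Choice of test.** Trials with no effect were simulated at 50 and 100 per arm, 2,500 per setting, so the Monte Carlo standard error is about sqrt(0.05 × 0.95/2,500) = 0.4 percentage points. A fixed rule (Kruskal-Wallis if a Shapiro-Wilk test on residuals rejects normality, otherwise ANOVA) was compared with running both tests and keeping the smaller p.

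| Distribution | Fixed rule, 50 / 100 per arm | Smaller p, 50 / 100 per arm |
|---|---|---|
| Normal | 4.6% / 5.1% | 5.4% / 5.9% |
| Lognormal, SD of log 0.5 | 4.5% / 5.6% | 6.4% / 7.4% |
| Lognormal, SD of log 1 | 4.1% / 4.9% | 6.6% / 8.1% |
| t with 3 df | 5.2% / 4.6% | 6.6% / 6.3% |

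With assumed real effects at 100 per arm (2,000 trials each), the two tests disagreed on significance in about 5% of trials for normal data, 16% for lognormal with SD of log 0.5, 21% for t with 3 df, and 56% for lognormal with SD of log 1. These rates show that the choice can change a result. They are not error rates of the plan.

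**The case against.** The strongest reply is that the SAP already plans the right analysis. ANCOVA with baseline and centre stands in the same paragraph as the default, and Protocol section 8 calls volume a main outcome, so 'main/important' can be read to cover it. This reading is possible, and it is why the point on volume is conditional. But the model is detailed only for mRS, and the volume item names none.

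A reader might infer that the collected baselines go unused. They do not: SAP 5(5)2) and 3) compare changes from baseline. ICU and hospital days have no baseline to use. The fair criticism is inefficient use and no centre term.

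A reader might also infer that the trial's verdict hangs on a test chosen after the fact. The only superiority rule the SAP states is the least-squares 95% confidence interval for mRS (SAP 3(2) and 5(5)1)), and the ANOVA or Kruskal-Wallis choice does not enter it. Nor do the documents say that the choice will be made unblinded, or by p-value. The SAP ties it to the distribution, and such a rule, once fixed, keeps the error rate near 5%.

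The efficiency loss may also be small for volume. In an illustrative simulation with entry volumes spread evenly over the 10-45 ml inclusion range and most haematomas not growing, the baseline correlation was about 0.82. The formula then gives about 76% power instead of 80%. This stands: the 62% end of the range is less plausible for volume. The documents give no correlation for any outcome.

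Finally, GCS is a ranked score, and SAP 4(3) sends ranked data to a CMH test, so the default for measurement data may not apply to it.

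**Conclusion.** The point holds as a gap in scope and specification. Outside mRS, the SAP does not commit to the adjusted analysis that it uses there. Coagulation, platelets and, unless it counts as 'main/important', haemorrhage volume get an unadjusted change-score comparison by a test with no stated selection rule.

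If ANCOVA would give 80% power, the loss is about 2 to 18 percentage points for correlations from 0.9 down to 0.3. This assumes equal variances at both times and a linear relation with baseline. The gain from a centre term cannot be sized from the documents.

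The missing test-selection rule is the lesser part. The 6-8% type I error on skewed or heavy-tailed data is a ceiling for an analyst who runs both tests and keeps the better one, which the SAP does not propose. The mRS superiority conclusion is untouched.

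**What to change.** In SAP 4(3) and 5(5):

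1. State that haemorrhage volume is analysed by the SAP's ANCOVA: follow-up value on arm, day-0 value, centre and operation. With the day-0 value as a covariate, analysing the change gives the same treatment effect, so the SAP's change-score presentation can stay.
2. Extend the same ANCOVA to coagulation and platelets.
3. Name one test in advance for each remaining outcome. Examples are a centre-stratified rank test for ICU and hospital days, and the SAP's CMH approach stratified by centre for GCS. Other pre-named tests would serve as well.
4. Delete the clause that lets the observed distribution select the test.

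The cost is SAP wording only. Protocol section 8 already schedules the day-0 values, so no new data or visits are needed. The analyst gives up the freedom to switch tests.
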